Patients will be asked to rate their average level of pain in the past week on an 11-point scale (0-10) at baseline and at every time point as listed in table 1

Beck Anxiety Inventory (BAI): 21-item self-report inventory for measuring the severity of anxiety with high internal consistency. Each of the 21-items is rated on a 4-point Likert scale indicating how much each symptom bothered the patient in the previous month. This is a reliable and validated self-reported measure of anxiety. This will be performed at baseline, visit 7 and visit 10.

Postoperative Nausea and Vomiting Intensity scale (PONV): This is a 4-item questionnaire that is a valid, reliable, and responsive measure of clinically important postoperative nausea and vomiting. This will be performed at baseline, visit 2, 3, 4 and visit 9.

Revised American Pain Society Patient Outcome Questionnaire (APS-POQ-R): This questionnaire measures 6 aspects of patient quality including 1) pain severity and relief, 2) impact of pain on activity, sleep, and negative emotions, 3) side effects of treatment, 4) helpfulness of information about pain treatment, 5) ability to participate in pain treatment decisions, and 6) use of nonpharmacological strategies. This is a reliable, validated, and feasible questionnaire with high internal consistency. This will be performed at visit 3, 4 and 5.

Daily symptom surveys: Post-operative days 0-6, patients will complete a sheet with 16 questions about pain intensity, nausea, vomiting, and mobility. This will be performed at each visit starting at visit 4 through visit 9.

Patients will receive general anesthesia and post-operative analgesia per standard of care for liver transplantation.

Screen failures:

Subjects that are unable to complete visit 2 assessments, within the allotted window, will be a screen failure. Follow-up assessments will not be performed on screen failure subjects. However, subjects randomized to the device may continue to wear the device through the 120 hours regardless of screen fail status.

Auricular Neurostimulation Application:

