Localized discomfort if the electrodes should become dislodged during the wearing of the device - Rare (event rate 1% - < 5%)

Localized dermatitis - Rare (event rate 1% - < 5%)

Drop in blood pressure - Rare (event rate 1% - < 5%)

Syncope (fainting) - Rare (event rate 1% - < 5%)

Adverse effects to supporting personnel

Skin piercing with percutaneous needles - Rare (event rate 1 % - < 5%)

There are numerous, possible direct and long-term benefits to the subjects in this study. The results of this study may provide important insights to the medical field regarding a new, non-pharmacologic therapy that could improve pain control and quality of life for patients undergoing liver transplantation. If effective, a significant decrease or prevention in post-operative opioid use would be a major breakthrough in healthcare. This treatment would then have the potential to be extrapolated to other post-operative settings and populations.

Data Analysis & Statistical Considerations

This randomized study and the subjects will be randomized 1:1 ratio to the treatment groups. The primary efficacy endpoint is opioid usage after surgery in the two groups, and the related secondary endpoint is pain score in the two groups at the end of surgery. Normality possible transformations to attain normality of these variables will be assessed. These variables will be analyzed using either a two-sample t-test or non-parametric Wilcoxon test, depending on whether the outcomes are normal or non-normal. Analysis will be conducted under Intent-To-Treat (ITT), and any missing outcome will be imputed under missing at random (MAR) using multiple imputation methods. In addition, complete case analysis will be conducted. Continuous outcomes, adjusted for covarites, will be examined using regression analysis. Significance of the results will be examined at a two-tailed 0.05 alpha level.

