Other secondary outcomes are: postoperative nausea and vomiting, postoperative ileus, postoperative immobility, length of hospital stay, incidence of ileus and time to return of bowel function, time to physical function, complications, and re-hospitalization. Continuous variables here will be analyzed using two-sample t-test or non-parametric Wilcoxon test, depending on whether the variables are normal or non-normal; categorical variables will be compared using chi-squared tests; time to event analysis will be examined using Kaplan-Meier curves. In addition, adjusted continuous outcomes will be examined using regression analysis; adjusted dichotomous outcomes will be examined using logistic regression; and adjusted time-to-event analysis will be examined using Cox proportional models. These analyses are exploratory, and significance will be assessed with and without adjusting for multiple testing.

Adverse events of this trial are infections and complications. Rates of infections and complications between the groups will be examined using Fisher's exact test or Chi-squared test.

Power: At the least (without any research funding) 25 subjects each will be randomized to the treatment groups. At alpha = 0.05 and 80% power and 25 subjects randomized to treatment groups, we should be able to observe effect size of about 0.81 between the two groups on the outcome of opioid usage; if we secure external funding, we should be able to randomize at least 32 subjects to each of the treatment groups. With 32 subjects in each groups, at alpha = 0.05 and 80% power, we should be able to observe effect size of 0.71 between the two groups. If we assume a 20% dropout rate, with the above sample sizes, we would observe effect sizes between .69 and 0.80 (Cohen, 1988).

Analysis will be conducted using statistical software SAS 9.4 (SAS Institute, Inc., Cary, NC).

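### Pain after the end of surgery has no stated analysis, and nausea and vomiting has no time point or summary, although both are scored repeatedly

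*Combined protocol and SAP*

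**What the plan says.** **Collection** (Study Interventions, Technical Details). The 0-10 pain rating is taken at baseline and at every time point in Table 1, which is not in the available text. For the PONV scale: "This will be performed at baseline, visit 2, 3, 4 and visit 9". The daily sheet has items on pain intensity, nausea, vomiting and mobility. It is assigned to post-operative days 0 to 6, and then: "This will be performed at each visit starting at visit 4 through visit 9". The day-30 telephone call (Intraoperative and Postoperative Protocol) repeats the pain rating, the symptom survey and the PONV score.

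**Analysis** (Data Analysis & Statistical Considerations). After the primary endpoint of opioid usage, "the related secondary endpoint is pain score in the two groups at the end of surgery", tested by t-test or Wilcoxon. Nausea and vomiting is listed among the other secondary outcomes, for which "Continuous variables here will be analyzed using two-sample t-test or non-parametric Wilcoxon test". Adjusted regression is added for continuous outcomes in both places. The other secondary analyses are labelled exploratory and are reported with and without a multiplicity adjustment. Missing outcomes are to be multiply imputed under MAR, with a complete-case analysis in addition.

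**Aim** (Design & Procedures). The study is to determine efficacy in reducing both pain and opioid use. Stimulation runs for 120 hours.

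**The concern.** A two-sample test needs one value per patient. For pain the plan supplies one, at the end of surgery, and is silent on every later score. Those later scores are the ones that show whether pain was lower while the device was running. For nausea and vomiting the plan supplies several values per patient and does not say which one, or which combination, enters the test.

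Two things are at stake. The first is precision: with as few as 25 patients per arm, a comparison that uses several correlated values can detect a smaller effect than one that uses a single value, with no new data. The second is credibility: the control arm receives standard care and no sham device is described, so a visit or summary left open now could be chosen later by someone who has seen patient-reported results by arm.

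**Working it through.** **1. Collected against analysed**

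| Score | Collected | Analysis named |
|---|---|---|
| 0-10 pain rating | baseline, each Table 1 time point, day 30 | end of surgery only |
| PONV scale | baseline, visits 2, 3, 4, 9, day 30 | two-sample test, no visit or summary |
| Daily sheet, pain item | days 0-6 or visits 4-9, day 30 | none |
| Daily sheet, nausea and vomiting items | as above | at most the PONV rule, no visit or summary |
| Daily sheet, mobility items | as above | times to chair and to walking, so used across days |

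No mixed model, GEE, area under the curve, peak or mean over days is named. The adjusted regression is not described as allowing for several values per patient.

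**2. The plan's own figures**

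Inputs: "Significance of the results will be examined at a two-tailed 0.05 alpha level"; 80% power; 25 or 32 per arm. The plan states "we should be able to observe effect size of about 0.81 between the two groups on the outcome of opioid usage" and "With 32 subjects in each groups, at alpha = 0.05 and 80% power, we should be able to observe effect size of 0.71".

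- Normal approximation, (1.960 + 0.842) × √(2/n): 0.79 at n = 25 and 0.70 at n = 32.
- Noncentral t: 0.809 at n = 25 and 0.7115 at n = 32. Both stated figures reproduce.

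These figures are for opioid usage; none is given for pain or PONV. I use them as the benchmark for any test on one value per patient. I do not use the plan's dropout range. A 20% loss leaves 25 × 0.8 = 20 and 32 × 0.8 = 25.6 per arm, which give 0.91 and 0.80, not .69 and 0.80. That is a separate matter.

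**3. Effect of averaging**

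Assumptions not in the documents: k values per patient with equal variance and common correlation ρ of 0.3, 0.5 or 0.7, and the same effect at each time. I take k = 4 (the four PONV visits, treated as post-operative) to k = 7 (days 0-6).

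Variance of the patient mean relative to one value: VR = (1 + (k − 1)ρ)/k. Detectable effect in single-day SD: d × √VR.

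| k | ρ | VR | √VR | 25 per arm (0.809) | 32 per arm (0.7115) |
|---|---|---|---|---|---|
| 4 | 0.3 | 1.9/4 = 0.475 | 0.689 | 0.56 | 0.49 |
| 4 | 0.5 | 2.5/4 = 0.625 | 0.791 | 0.64 | 0.56 |
| 4 | 0.7 | 3.1/4 = 0.775 | 0.880 | 0.71 | 0.63 |
| 7 | 0.3 | 2.8/7 = 0.400 | 0.632 | 0.51 | 0.45 |
| 7 | 0.5 | 4.0/7 = 0.571 | 0.756 | 0.61 | 0.54 |
| 7 | 0.7 | 5.2/7 = 0.743 | 0.862 | 0.70 | 0.61 |

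The pain rating asks about the past week, so successive daily windows overlap. That pushes ρ for this score towards the upper rows.

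**4. When averaging loses**

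If the effect is present on only m of k days, the average carries m/k of it. Averaging beats a test on one affected day, known in advance, only if m/k > √VR. For k = 4 that needs 3 of 4 days at ρ = 0.3 (0.75 > 0.689) and all 4 at ρ = 0.5 or 0.7. For k = 7 it needs 5, 6 or 7 days at ρ = 0.3, 0.5 or 0.7.

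**The case against.** **A two-sample test can be valid here.** A t-test or Wilcoxon test on a per-patient mean, area under the curve or peak fits the sentence on other secondary outcomes. The gain shown above is itself that of a two-sample test on a mean. This stands. A reader might infer that the plan must either throw away most of its values or test each visit separately; the text forces neither. What is missing is the choice.

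**Naming one time for pain is a legitimate choice.** It is, and the sentence on continuous variables covers the other secondary outcomes, not pain. But it leaves later pain without an analysis in a trial that says it will assess pain reduction.

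**False positives.** A reader might infer an inflated error rate from visit-by-visit testing. No such testing is planned, and the nausea and vomiting analyses are exploratory and reported with and without multiplicity adjustment.

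**Missed sheets.** A reader might infer that a patient who misses one sheet drops out of that comparison. The plan imputes missing outcomes, and nothing stops the imputation from using neighbouring days.

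**The gain is assumed.** This also stands. The correlations and the equal daily effect are assumptions, and the number of values is uncertain because Table 1 is not in the text and the schedules disagree.

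**A mixed model drops the plan's provision for non-normal scores.** This is fair, so the fix needs a non-parametric fallback.

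**Conclusion.** The point holds as a gap in the secondary analyses. Post-operative pain beyond the end of surgery has no stated analysis, and nausea and vomiting has a test but no time point or summary. A better analysis is available from data already planned. With 4 to 7 values, ρ between 0.3 and 0.7 and a similar effect across days, the detectable effect at 25 per arm falls from 0.81 to about 0.51-0.71 single-day SD. A short-lived effect would be diluted, by the break-even in step 4 of the working.

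The documents do not support anything stronger. The primary opioid endpoint and its power statement are untouched, and the survey's mobility items are used through the times to chair and walking. The change should be made before analysis, but the trial's main conclusion does not depend on it.

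**What to change.** In Data Analysis & Statistical Considerations:

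1. Analyse each repeated score (post-operative pain, PONV, daily-sheet nausea) with one repeated-measures mixed model: arm, day, arm-by-day, and the baseline value where collected. State the covariance structure and a fallback in advance.
2. Make the arm difference averaged over the post-operative days the single reported contrast, and show by-day differences descriptively, so that a short-lived effect remains visible. List the days in the average and say whether day 30 is one of them.
3. If scores are clearly non-normal, use a Wilcoxon test on the per-patient mean or area under the curve instead.
4. Keep the end-of-surgery pain comparison as listed.
5. Reconcile the schedules. The Experimental Design paragraph puts PONV and the symptom surveys on device days 1-5. Technical Details puts PONV at visits 2, 3, 4 and 9, and the survey on days 0-6 (seven days) but at visits 4-9 (six visits). The former also names a VAS after baseline where the latter uses the 0-10 rating with past-week recall. State which pain measure and recall period the model uses.

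The cost is some SAP wording and one mixed-model program, with no new visits or data.

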Auricular neurostimulation is a potential novel and non-invasive method of pain control following liver transplantation in a growing patient population with the probability of significant impact on economics and morbidity. We propose a pilot study to investigate the effects of auricular neurostimulation in patients receiving a liver transplantation. We will investigate the effects of auricular neurostimulation with this novel device and compare it to the current standard of care for pain management following liver transplantation.

The BRIDGE device is an FDA-approved (510(k)140530) and commercially available device manufactured by Key Electronics (Jeffersonville, IN, USA) and distributed by Innovative Health Solutions (Versailles, IN, USA). BRIDGE is an ambulatory, neurological device which consists of a battery powered, externally affixed generator with 4 wire leads attached to 3 electrode/needle arrays and one single point needle. The arrays are designed to produce a field effect similar to surgically implanted peripheral neurostimulators. One BRIDGE device per patient will be used in this study. The electrodes will be placed percutaneously in the external ear with the help of a transilluminator to visualize the neurovascular

bundles. The BRIDGE device has recently been approved by the U.S. Food & Drug Administration for use in accupuncture.

Design & Procedures

This is a prospective, randomized study to determine the efficacy of the BRIDGE device in reducing pain and opioid use in patients following liver transplantation. Subjects will be randomized in a 1:1 ration to one of the below groups:

Group 1: BRIDGE device will be placed by a physician prior to start of the surgery with standard of care pain control analgesia

Group 2: Subjects will receive the standard of care pain control analgesia

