Patients currently or awaiting listing for a liver transplant will be prescreened by study personnel prior to their clinic. A member of the clinical care team known to the potential subject will introduce the study and/or study personnel once initial eligibility is confirmed. All patients eligible for liver

transplantation will be assessed for eligibility and potential study participation. All transplant patients undergo social and psychological evaluation prior to transplant. The clinical and study team will address any cognitive issues prior to transplant. Subjects that signed consent greater than 1 month prior to transplant will be contacted at the time of transplant notification to confirm continued desire to participate. Patients with liver failure may also experience liver encephalopathy that would impair their ability to consent. For subjects experiencing hepatic encephalopathy we will consent their legally authorized representative prior to transplantation. Subjects will be re-evaluated following the liver transplant procedure for consent appropriateness. We anticipate enrolling 35 participants in each group, for a total of 70 subjects. We will exclude pregnant females form this study as part of clinical standard of care for liver transplantation.

Inclusion criteria:

≥18 years of age but < 70 years of age

Actively listed for isolated liver transplantation

Subject or legally authorized representative able to sign informed consent

Not currently treated with opioids or any medications that may interact with opioids

English speaking

Willing and able to participate and consent to this study

Exclusion criteria:

Diagnosis of acute liver failure or primary sclerosing cholangitis (PSC)

Anticipated that the subject will require a new roux-en-y hepaticojejunostomy

Current use of opioid use or other substance abuse.

Chronic pain disorders

Need for regional anesthesia (regional nerve blocks or epidurals)

Adhesive allergy/sensitivity

Subject admitted to the ICU at the time of transplant

Pregnancy

Subjects who meet eligibility and sign the consent form will be eligible to be enrolled into the study at the time of transplant. All eligible subjects will be recruited from Duke Transplant clinics or during hospital admission prior to transplant.

Study Interventions

Technical Details

Subjects will prospectively complete the following questionnaires at different time points during the study (see Table 1 for timeline):

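### Adjusted yes/no outcomes in 50 to 70 patients are planned with logistic regression and no sparse-data version; Firth's method would be a cheap, minor improvement

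*Combined protocol and SAP*

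**What the plan says.** The section Data Analysis & Statistical Considerations lists secondary outcomes that include ileus, complications and re-hospitalisation. Categorical outcomes are compared by chi-squared tests. In addition, "adjusted dichotomous outcomes will be examined using logistic regression". The section calls these analyses exploratory. For infections and complications it offers Fisher's exact test or a chi-squared test, both unadjusted.

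Three sample sizes appear. The Power paragraph gives a minimum: "At the least (without any research funding) 25 subjects each will be randomized to the treatment groups". With external funding the aim is to "randomize at least 32 subjects to each of the treatment groups". Selection of Subjects states: "We anticipate enrolling 35 participants in each group, for a total of 70 subjects". The total is therefore 50, 64 or 70.

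The documents do not give an expected rate for any yes/no outcome, name or count the adjustment covariates, or say what happens if a group has no events. Ileus is defined under Intraoperative and Postoperative Protocol by more than 48 hours of nasogastric decompression, again without an expected rate.

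**The concern.** Unqualified, logistic regression means maximum likelihood. With few events, that method has two known weaknesses:

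- **Separation.** If one group has no events, or the covariates split events from non-events, the odds ratio has no finite estimate and the Wald test is unusable.
- **Small-sample bias.** When the fit does converge, a real effect tends to be estimated too far from the null.

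The plan allows for small counts in the unadjusted comparison of complications but has no counterpart for the adjusted model. If separation appears, the analyst must choose a remedy after seeing the data. What is at stake is the adjusted odds ratio for a few secondary outcomes, one of which (complications) the plan also treats as a safety measure.

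**Working it through.** **Inputs from the documents.** 25, 32 or 35 per group; 1:1 allocation; two-sided alpha of 0.05.

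**Assumed, because not given.** Control event rate of 10%, 20% or 30%. Device odds ratio 0.5, so the true log odds ratio is -0.69. Treatment group plus one to three covariates, each with odds ratio 1.5 per SD in the three-covariate runs.

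**Step 1: the plan's own figure.** The only power statement concerns a continuous outcome: "we should be able to observe effect size of about 0.81 between the two groups on the outcome of opioid usage". The normal approximation, d = (1.960 + 0.842) x sqrt(2/n), gives 0.792 at 25 per group and 0.700 at 32. The exact t calculation gives 0.809 and 0.712, so the plan's 0.81 and 0.71 are reproduced. They say nothing about yes/no outcomes.

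**Step 2: expected events.** With control rate p0, the device odds are 0.5 x p0/(1 - p0). Control rates of 10%, 20% and 30% give device rates p1 of 5.26%, 11.11% and 17.65%. Expected events are n x (p0 + p1):

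| Control rate | 25 per group | 32 per group | 35 per group |
|---|---|---|---|
| 10% | 3.8 | 4.9 | 5.3 |
| 20% | 7.8 | 10.0 | 10.9 |
| 30% | 11.9 | 15.2 | 16.7 |

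A model with intercept, group and three covariates has five coefficients. That is 3.8/5 = 0.8 to 16.7/5 = 3.3 events per coefficient.

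**Step 3: chance of no finite estimate.** If a group has no events, the group odds ratio is not finite, whatever the covariates. The probability is 1 - [1 - (1 - p0)^n] x [1 - (1 - p1)^n]. At 10% and n = 25: 1 - (1 - 0.0718)(1 - 0.2588) = 0.312.

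| Control rate | 25 per group | 32 per group | 35 per group |
|---|---|---|---|
| 10%, exact, group term only | 31% | 21% | 17% |
| 10%, simulated, 3 covariates | 33% | 21% | 17% |
| 20%, exact, group term only | 5.6% | 2.4% | 1.7% |
| 20%, simulated, 3 covariates | 5.5% | 2.1% | 1.4% |
| 30%, exact, group term only | 0.8% | 0.2% | 0.1% |

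If 10% is instead the rate for a control patient with average covariates, the overall rate is higher. Failures then fall to about 24% at 25 per group and about 11% at 35.

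Two less favourable settings lie outside these assumptions:

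- With the risk halved (20% to 10%), two or four covariates of which half are binary, and any non-finite coefficient counted, failures were 11-15% at 25 per group and about 4% at 35.
- The plan's 20% dropout would leave 25 x 0.8 = 20 per group in the complete-case analysis. The exact formula then gives 42% at a 10% control rate and 10.5% at 20%.

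**Step 4: bias among finite fits.**

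- 20% control rate, three covariates: mean -0.80 to -0.82 against -0.69, which is 15-18% too large.
- 30%, three covariates: 11-13% too large.
- 20-30%, one covariate: -0.70 to -0.75, which is 1-8% too large.
- Risk halved, two or four covariates: 3-16% too large at 20% and 7-24% at 30%.
- 10%, three covariates: -0.57 at 25 per group and -0.65 at 35, towards the null. The trials lost as non-finite are mainly those with no device-group events, which point to the largest effects.
- No true effect: mean within 0.04 of zero, and Wald rejection of 1-6% against a nominal 5%.

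With root mean square error near 1 and 1,000 to 1,500 runs, the simulation error of a mean is about 0.03, or 4-5% of 0.69. The percentages are therefore good to a few points, and roughly 5-25% is a fair summary for the 20-30% rates.

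**Step 5: Firth's method, three covariates.** Mean estimates are -0.67 to -0.74 at 20% and 30%. At 20%, root mean square error at 25/32/35 per group is 0.94/0.80/0.75, against 1.09/0.92/0.86 for maximum likelihood. The reductions are 1 - 0.94/1.09 = 14%, 1 - 0.80/0.92 = 13% and 1 - 0.75/0.86 = 13%. With the risk halved from 10% to 5%, Firth gave -0.65 to -0.73 against -0.75, a slight shrinkage.

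**The case against.** The strongest reply is that every figure on event rates and covariates is supplied from outside the plan. A reader might infer that the adjusted models will often fail. The documents do not support that: failure is common only at control rates near 10% or below, and no rate is given.

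A reader might also infer that the analysis must either fail or exaggerate the device effect. That does not follow either. The two problems occur at different event rates, and with no true effect there is no systematic bias, so the method does not create a spurious benefit. At 20-30% the bias is about 0.1 on the log scale, against a root mean square error of roughly 0.7-1.1.

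The adjusted models are exploratory additions to unadjusted tests, and Fisher's test is already offered for complications. The wording does not forbid a penalised fit. The unnamed covariate set partly determines the size of the problem, and changing the fitting method does not fill that gap. Finally, missing outcomes are to be multiply imputed, and profile-likelihood limits do not pool directly across imputed data sets.

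All of this stands, and it limits the point to a minor one. It does not defend the clause as written. The smaller root mean square error shows a gain beyond the removal of a small bias, and a method named in advance avoids a post hoc choice when a group has no events. The imputation objection is met by a pooling rule in the fix.

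**Conclusion.** The point holds as a minor, inexpensive improvement. Its size depends on a device odds ratio of 0.5, one to three covariates and control rates of 10-30%, none of which the documents state. The practical risk is an unusable adjusted odds ratio if events are rare, or a modestly inflated one if they are moderately common and the device works. The primary endpoint (opioid usage), the unadjusted comparisons and the power figures are unaffected. The evidence for Firth's advantage in root mean square error comes from the three-covariate setting; with a single covariate, maximum likelihood has little bias to correct.

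**What to change.** In the clause on adjusted dichotomous outcomes, replace *logistic regression* with: *Firth penalised-likelihood logistic regression (FIRTH option, SAS 9.4 PROC LOGISTIC), with profile-likelihood confidence limits in the complete-case analysis and Rubin's-rules pooling of the Firth estimates where outcomes are imputed*. Apply it to every dichotomous outcome, so that the choice does not depend on whether separation is seen.

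The cost is one sentence and one option in the software already named. There are two downsides: slight shrinkage towards no effect when events are very few, and a separate interval method for imputed data. Naming and limiting the covariates would be a sensible companion change, because Firth's method does not settle which covariates enter the model.
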